- 4. Determine the fidelity of all intervention components, and explore any identified patient, provider (physician, nurse, health coach), and/or health system barriers to implementation.
- 5. Assess the costs associated with implementing the ACP intervention from a health system perspective.

Study Design and Procedures

We will conduct a 2-arm, patient-randomized, pragmatic trial among 750 patients in Arkansas with type 2 diabetes to test the effectiveness and fidelity of a multifaceted, health coachled, low literacy, self-management intervention to improve behavioral and clinical outcomes compared to enhanced usual care in level 3 patient centered medical homes. Enhanced usual care differs from standard diabetes care because enhanced usual care includes patient resources associated with PCMH (team-based care, electronic health records, and care coordination). Eligible, consented patients will be followed for 1 year post baseline interview. Those receiving the ACP intervention will be administered the ACP health literacy strategy at baseline, with 'frontloaded' telephone or in-person follow-up education approximately every 3 months, counseling and action-planning occurring at approximately 2 weeks, 4 weeks, and 8 weeks and then monthly between guarterly clinical visits. In-person, 'point-of-care' counseling sessions will occur guarterly, coinciding with diabetes routine clinical visits. We intentionally aimed to optimize the number of 'touch points' over 1 year, taking into account a reasonable workload for health coaches. Addressing Aim 3, which seeks to ascertain the minimum number of action plans necessary to achieve clinical diabetes goals, or an increasing benefit is seen with more touch points (no threshold). Primary outcomes include intermediary biomarkers indicative of proper disease selfmanagement (HbA1c, blood pressure, LDL cholesterol). In addition, secondary outcomes to be measured include diabetes and treatment-related knowledge, self-efficacy, disease-related distress and quality of life, activation, health behaviors and health services utilization. To determine the reliability and costs associated with delivering the intervention, we will also closely monitor the implementation process and evaluate the fidelity of the components and strategies.

		hanced Usual Care and Intervention
	STANDARD	DIABETES MEDICAL CARE
		In Both Arms
Care Management	of medical care	rting
		AND SELF-MANAGEMENT SUPPORT
	'Enhanced" Usual Care Arm	Intervention Arm

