Follow-Up	 Follow-up at scheduled clinic visits approximately every 3 months No standard, practices vary over time 	 In-person 15 min education & counseling sessions at approximately 3,6, 9, and 12 months with health coach Phone calls with health coach to inquire about progress on action plans, use motivational interviewing to problem-solve or establish new action plans Bi-weekly post-visit phone calls for first 3 months (2,4, and 8 weeks after baseline encounter) Monthly post-visit phone calls between clinic visits after 3 months (4,5,7, 8, 10, and 11 month calls) Survey data will be collected at baseline, 3 and 6 months; clinical data will be collected following baseline, 3, 6, 9, and 12 months
Clinical Integration	 Documentation in EHR with nursing note whether post visit DM counseling occurred (yes or no) and when 	 EHR tools and prompts for health coach follow-up phone calls or face-to-face meetings, documentation of call attempts Health coach received information on patients' glycemic control (HbA1c lab value at visit) prior to patient counseling session Health coach documents in EHR every month using care note function: describes and provides update for PCP detailing patient's diabetes action plans and progress towards goals Email to PCP via EHR if patient does not complete 2 consecutive action plans, identifying barriers is known, or if any concerns arise

Figure 1. Study flow chart

Study Sites

The project will engage six UAMS Regional family medicine clinics in regions of Arkansas that are underserved and rural. All clinics have implemented the Patient-Centered Medical Home (PCMH) model of care and achieved the highest level of accreditation, level 3. All regional medical centers have participated in implementation of health literacy best practices using the Agency for Healthcare Quality and Research (AHRQ)'s Health Literacy Universal Precautions Toolkit for the last two years. The majority of patients served by these clinics is low-income and there is a high rate of chronic disease in each clinic's patient population. There are approximately 2,205 total patients at these clinics with HbA1c greater than 7.5%, which denotes that an individual has perhaps not yet achieved tight glycemic control and therefore may be at elevated risk for diabetes-related complications. All clinics have agreed to participate. Letters of support from the clinic directors are included.

Preliminary Studies

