or they can get it at the 6 month visit, whatever is convenient for them. We considered alternative randomization schemes, including physician and clinic-level randomization, but our team carefully determined randomization at the patient level to be the most rigorous and appropriate approach. Physician level-randomization was viewed as not feasible since patients at these practices frequently see multiple providers (attendings and residents) over the course of a year, and are not 'bonded' to just one physician. Clinic-level randomization was also viewed as not an option given too few sites to assign, and the considerable diversity still seen across these practices, by size, staffing and patient population that would make it unlikely to have equivalent study arms.

Blinding. As with most behavioral interventions, it will not be possible to fully blind researchers, healthcare providers, and study subjects to intervention vs. enhanced usual care assignments. However, we have purposefully designed our trial to prevent certain threats to contamination between study arms. Patients will be told they will receive one of two models of diabetes education and self-management support. While they will not be deliberately made aware of the approach not received, we do recognize that there is an unavoidable risk of patients learning from other patients involved in the study. Similarly, physicians and other prescribers will not be intentionally made aware of their patients' study assignments. However, it is very likely that as health coaches will be trained to include monthly progress notes on patients' action plans in the EHR for providers to read, enrollment status to arm will be recognized. But neither patient nor healthcare provider will have access to any of the intervention components, as that solely resides with the health coach who will only be serving intervention patients, having no role with enhanced usual care subjects for the term of the trial. This commitment has been strongly made by UAMS and clinic leadership (see Letters of Support).

Qualitative provider/clinic barriers and facilitators to implementation

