Diabetes Distress. The Diabetes Distress Scale (DDS) is a 17-item measure of diabetesrelated emotional distress. It has four subscales corresponding to emotional burden, physicianrelated distress, regimen distress, and diabetes interpersonal distress.

Quality of Life. Patient-Reported Outcomes Measurement Information System (PROMIS) physical health (function) short form along with the PHQ-9 Depression Scale will be collected. Nurses will be notified if patients' scores indicate the need for follow-up either by the PCP or PCBHF, based on existing clinic protocol.

Clinical Outcomes

Hemoglobin A1c (HbA1c) and LDL cholesterol lab values, along with systolic and diastolic blood pressure values are collected as part of routine clinical care approximately every 3 months, and will be recorded from the medical record following each visit. *Body Mass Index.* Height and weight will also be taken from the medical record and the standard calculation for BMI applied (kg/m²). In addition, weight (in lbs.) will be recorded separately for weight gain/loss as an additional outcome.

Health Services Use

We will ask patients to self-report emergency department/urgency care visits, and hospitalizations. Dates of clinic appointments during the study period may be recorded from the medical record.

Fidelity outcomes:

Receipt of Diabetes Materials

We will ask patients whether they received all of the diabetes materials (yes/no), and if they still have them at each follow-up encounter (3 and 6 months).

Receipt of nurse/health coach counseling

We will ask patients to self-report whether their health coach/nurse reviewed the diabetes materials and/or provided counseling. Using health coach logs, we will document for each follow-

up time interval, whether the patient was reached (yes/no), and if yes, the time spent with the patient.

Provider-Patient Communication

We will ask questions adapted from the Consumer Assessment of Health Providers Survey (CAHPS)⁴¹ to evaluate the extent and quality of nurse/health coach counseling.

Perceived Helpfulness

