Baseline characteristics and demographics will be summarized overall and by clinic using descriptive statistics (mean \pm standard deviation for continuous variables, frequencies and percentages for categorical variables, and medians/quartiles as appropriate for ordinal variables). Analyses across all relevant outcomes (i.e., those corresponding to H₁-H₆) will mirror one another in general, with primary outcome being defined as HbA1c levels at six months. Secondary outcome measures include disease and treatment knowledge scores, self-efficacy scores, adherence to self-care behaviors, diabetes-related distress, diabetes-related quality of life and other clinical outcomes (blood pressure, LDL, cholesterol, BMI). Survey data will be collected at baseline, 3 and 6 months; clinical data will be collected at baseline, 3, 6, 9, and 12 months. The primary time point of interest for H₁-H₅ is three-month follow up and for clinical outcomes (H₆) is six-month follow-up, but subjects will be followed through 12 months in order to examine sustainability. We will assume missing data are missing at random, and analyses will consist of parametric statistical tests. Relevant statistical assumptions will be assessed as appropriate, and nonparametric analyses and/or transformations of variables will be explored in the event of violations.

Aim 1 analysis for each outcome will consist of an analysis of covariance (ANCOVA) in which overall mean (μ) follow-up outcome (e.g., HbA1c at 6 months) across groups will be modeled as follows:

$$\mu_i = \beta_0 + \beta_1 I(ACP intervention_i) + \beta_2 (Baseline_i) + \epsilon_i,$$

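### The six-month primary HbA1c is a routine-care value with no common window and no tie to the six-month study contact both arms already have, so its timing and availability could differ by arm

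*Combined protocol and SAP*

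**What the plan says.** **Outcome and source.** The Data Analysis section has the "primary outcome being defined as HbA1c levels at six months". Under Clinical Outcomes, LDL, blood pressure and HbA1c results "are collected as part of routine clinical care approximately every 3 months, and will be recorded from the medical record following each visit". No section gives a window around month six, a rule for choosing among several values, or a fallback if no test was done. Under Health Services Use, recording of clinic appointment dates is optional.

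**Contacts in each arm.** The table comparing the arms (Follow-Up row) gives enhanced usual care "Follow-up at scheduled clinic visits approximately every 3 months", followed by "No standard, practices vary over time". The intervention column has "In-person 15 min education & counseling sessions at approximately 3,6, 9, and 12 months with health coach", scheduled phone calls and, under Clinical Integration, "EHR tools and prompts for health coach follow-up phone calls or face-to-face meetings, documentation of call attempts". Study Design and Procedures says that in-person "counseling sessions will occur guarterly, coinciding with diabetes routine clinical visits".

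**Shared research contacts.** The Randomization section offers gift cards at baseline, 3 and 6 months without restriction by arm. It lets the 3-month follow-up take place by phone, in which case patients can collect the card at their next clinic attendance "or they can get it at the 6 month visit, whatever is convenient for them". The fidelity section also refers to 3- and 6-month encounters for patients in general. Data Analysis schedules surveys at baseline, 3 and 6 months and clinical data at baseline, 3, 6, 9 and 12 months for everyone.

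**Analysis.** The primary model is an ANCOVA of the follow-up value on arm and baseline value. Missing data are assumed missing at random. Linear mixed models are exploratory, multiple imputation is a sensitivity analysis, and pattern-mixture or selection models are to be explored if non-ignorable missingness is suspected.

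**The concern.** The primary value exists only if a routine visit took place near month six and HbA1c was drawn there. The intervention adds structured contact timed to those same visits. If that contact makes attendance more regular, intervention patients would have a six-month value more often, or closer to six months, than controls.

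Absence may also carry information. The protocol's background on health literacy says that patients with lower literacy engage less in regular care, and it lists missed appointments among the routes to worse outcomes. The same mechanism bears on the Aim 2 comparison by literacy level.

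At stake is the validity of the six-month contrast more than its precision. A patient without a six-month value adds nothing to the primary ANCOVA unless the value is imputed, and no planned analysis deals with measurement timing.

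**Working it through.** **1. The plan's own figure.** Inputs from Power and Sample Size Considerations: two-sample t-test, two-sided 5%, 337 per arm at six months, spread 1.9 (read as an SD), target 0.43 with 80% power.

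- SE = 1.9 × √(2/337) = 0.146.
- Detectable difference at 80% power = (1.960 + 0.842) × 0.146 = 0.41.
- Power for 0.43 = 83.6%.

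The stated 0.43 is therefore slightly conservative on this reading. Nothing below depends on that discrepancy.

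**2. Loss of precision alone.** The documents give no HbA1c capture rates, so these are assumed. Capture of 90% (intervention) and 80% (control) of 375 gives 337 and 300 patients and 81.4% power for 0.43. Capture of 90% and 70% gives 337 and 262 patients and 78.5% power. The loss is modest.

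**3. When bias arises.** The model conditions on arm and baseline HbA1c. If missingness depends only on those two, the complete-case ANCOVA is not biased by it. Bias needs missingness that also depends on six-month HbA1c given arm and baseline. The relevant gap is therefore what remains between unmeasured and measured patients after baseline adjustment. Eligibility limits recent HbA1c to 7.5-10%, which restricts the part of any raw gap that baseline explains.

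**4. Size of the bias (all inputs assumed).** Let m be the share unmeasured in an arm and g the residual gap (unmeasured minus measured), taken as equal in both arms. The full mean is the measured mean + m × g, so the measured mean is too low by m × g. Hence

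observed (control − intervention) = true (control − intervention) − (m_control − m_intervention) × g.

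| m_control | m_intervention | g | Bias | Share of 0.43 |
|---|---|---|---|---|
| 0.15 | 0.05 | 0.5 | 0.10 × 0.5 = 0.05 | 12% |
| 0.20 | 0.05 | 1.0 | 0.15 × 1.0 = 0.15 | 35% |

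With g positive, the benefit is understated. If the controls who go unmeasured are the well-controlled ones, g is negative and the benefit is overstated by the same amounts.

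**5. Consequence for the test (SE 0.146).** Under attenuation, a true 0.43 appears as 0.38 to 0.28.

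- 0.38/0.146 − 1.96 = 0.64, giving power of about 74%.
- 0.28/0.146 − 1.96 = −0.05, giving power of about 48%.
- With no true effect, a bias of 0.05 or 0.15 in either direction raises the two-sided error rate from 5% to 6.3% or 17.6%.

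These use the t-test SE at the planned 337 per arm. A smaller SE from ANCOVA would leave more power in the attenuated case, but would make the same bias larger relative to the SE.

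**6. Timing.** The documents give no HbA1c trajectory and no distribution of visit dates, so the effect of measuring one arm later than the other cannot be sized.

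**The case against.** A reader might infer that only the intervention arm has set contacts. The documents do not support that. Controls also have scheduled visits about every three months, and the 3- and 6-month encounters and gift cards are not limited by arm. The remark about no standard sits in a row that seems to concern education and self-management support, so it may not describe laboratory monitoring at all (the table is broken in the text).

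A reader might also infer that the intervention alters how HbA1c is measured. No section says that coaches book routine visits or order tests. Their sessions are meant to coincide with visits, and the record prompts are for coach calls and meetings. More regular attendance in that arm is possible, but it is not written into the plan.

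Two further readings go too far. The 90% retention cannot be shown to exclude HbA1c capture: the power section applies it to the primary outcome without saying what counts as retained. Nor is a spurious benefit the expected result, since the illustrated inputs give attenuation.

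The plan does take missing data seriously. It analyses all enrolled patients as randomised and lists mixed models, imputation with best- and worst-case scenarios, and models for non-ignorable missingness. It never uses the term complete-case; that follows from the form of the ANCOVA.

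What stands is that the shared six-month contact is not tied to an HbA1c draw, there is no common window, and the methods that would use the other HbA1c values are not primary.

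**Conclusion.** The concern holds as a weakness in how the primary outcome is obtained and analysed. It is not a demonstrated bias. Timing and availability of the six-month HbA1c could differ by arm, and the plan neither prevents this nor undertakes to report it.

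The illustrated 0.05-0.15 points rests wholly on assumed shares unmeasured and an assumed residual gap. Its sign depends on which patients go unmeasured. If the arms have similar capture, or if missingness depends only on arm and baseline HbA1c, this bias vanishes. The point deserves action because the remedy uses contacts and data that are already planned.

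**What to change.** 1. In both arms, hold the existing six-month research contact at the routine visit where HbA1c is drawn.
2. Define the primary value as the one closest to day 182 within a single window common to both arms, fixed before any data are seen by arm. With values about three months apart, half the spacing (3/2 = 1.5 months) on each side is the natural upper limit.
3. Make the primary analysis a longitudinal model, or multiple imputation, that uses the 3-, 9- and 12-month values already scheduled, with the six-month arm difference as the estimate. Missingness may then depend on other observed HbA1c values as well as arm and baseline. Keep the analyses for non-ignorable missingness as sensitivity analyses.
4. Report by arm the proportion with a six-month HbA1c and the distribution of its timing. This requires the date of each value to be recorded as a matter of course.
5. Reconcile Table 1, which lists interviews at 3 and 12 months, with the 3- and 6-month survey schedule elsewhere, because the first step relies on a six-month contact in both arms.

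The cost is scheduling effort, some analysis work and revised SAP wording. No study laboratory is needed. Follow-up becomes slightly less pragmatic.

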The two-day training developed by Drs. [name], [name] and [name] will be informed by previous staff training in community clinics using the ACP guide and brief counseling framework. The session will take place in a central location and will include discussion of roles and responsibilities of the health coach for this project, and a review of the counseling framework. Skill-building will focus on brief education and coaching to facilitate patients' setting health goals and creating highly specific and easily achievable action plans. Training will also include skill building in motivational interviewing, clear communication and use of health literacy best practices (slowing down, using plain language, reducing numeracy demands, pointing out key messages in the guide book and using teach-back to confirm understanding). The theory-based training is designed to improve health coaches' capacity to enhance patients' understanding of their disease and problem-solving ability to change their health behavior and adhere to their action plans. The training will also focus on effective telephone counseling and follow up, employing strategies developed in previous research to reach patients by phone. Instruction will also be provided on use of a tracking system to recorded number of contacts (phone and in person), length of time spent in each contact, number of attempts to reach patients, and the content of each session.

Nurse training will cover an overview of the usual care diabetes materials in the enhanced usual care arm only (the "Living Well with Diabetes: a self-care workbook"). A review of the standards for usual care delivery will be provided to avoid contamination, as well as training on the tracking system. This will be provided by the Director of Research for the family medical centers in collaboration with the study team.

Randomization. After the initial phone call to recruit participants, the RA will assign patients interested in participating to either the intervention or to the enhanced usual care arm based on an allocation table created prior to study recruitment using a simple 1:1 randomization scheme, stratified by site. Patients will receive a \$30 Walmart gift card at baseline, a \$30 Walmart gift card at 3 months and a \$30 Walmart gift card at 6 months for their participation. If the patient has a phone call for the 3 month follow-up, they can get their gift card the next time they come into clinic

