where *i* corresponds to the individual subject (*i*=1,...,*total N*), β_0 serves as an intercept, β_1 serves as the intervention effect [*I*(*ACP intervention*_i) is an indicator variable for active ACP intervention arm], β_2 represents the effect of baseline value of the corresponding outcome variable, and ϵ_i represents random error. Primary analyses will test the null hypothesis H_0 : $\beta_1 = 0$ against the twosided alternative at the 5% level of significance. Similar analyses will be employed for all relevant outcomes at three and/or six-month follow-up (to examine efficacy/effectiveness) and 12-month follow-up (to examine sustainability). Baseline variables (demographics, comorbidities, health literacy, etc.) will be explored one at a time, in turn, for association with outcome(s), and where appropriate, models will adjusted for significant baseline prognostic variables. Exploratory analyses will employ linear mixed effects models that include a fixed treatment arm, baseline value, relevant prognostic variables, and time effects along with a random subject effect in order

to account for within-subject association among outcome observations. Exploratory analyses will involve inclusion of a fixed change-point or spline term(s) to examine changes in slope over different time periods and/or higher order/interaction terms. In order to examine whether there may a difference across clinic, a random clinic effect will be examined as well, and where appropriate, subgroup analyses by clinic will be employed.

To address Aim 2 (H₇), the subjects will be classified by literacy level (lower literacy or higher literacy), and above analyses will be repeated within each arm but include an indicator for literacy group. Further, the primary model (above) will be modified to include a literacy level effect and corresponding arm-by-literacy level interaction term.

To address Aim 3, we will analyze only those subjects randomized to the ACP intervention arm. We will examine association of (a) number of contacts with each subject and (b) length of contact time, with each relevant outcome variable (H_1 - H_6) at follow-up via a linear model as above. Each model will include an intercept, baseline value for the relevant variable, and variable (a) and/or (b), along with any additional demographics/prognostic variables found relevant in Aims 1 and 2.

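### The primary ANCOVA leaves out site, the factor that stratifies randomisation; adding it is a nearly free gain in precision

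*Combined protocol and SAP*

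**What the plan says.** The Randomization paragraph (Study Design and Procedures) has patients allocated "using a simple 1:1 randomization scheme, stratified by site". Study Sites gives the number of strata: "The project will engage six UAMS Regional family medicine clinics". When it explains why whole clinics were not randomised, the protocol points to "the considerable diversity still seen across these practices, by size, staffing and patient population".

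The Data Analysis section says that analyses for H1–H6 "will mirror one another in general, with primary outcome being defined as HbA1c levels at six months". For Aim 1 it states: "Aim 1 analysis for each outcome will consist of an analysis of covariance (ANCOVA) in which overall mean". The printed equation has three terms: intercept, arm and baseline value of the outcome. The test of the arm coefficient is two-sided at 5%.

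Clinic enters later, among the exploratory mixed models: "In order to examine whether there may a difference across clinic, a random clinic effect will be examined as well". Clinic subgroup analyses may follow where judged appropriate. Separately, baseline variables are screened one at a time and "where appropriate, models will adjusted for significant baseline prognostic variables"; site is not named in that list. The Aim 2 paragraph refers back to the printed equation as the primary model: "the primary model (above) will be modified to include a literacy level effect".

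**The concern.** The protocol regards its clinics as different enough to stratify on, and in Power and Sample Size Considerations it counts on ANCOVA for extra precision. The primary model then leaves out the one other factor that the design itself singles out. Examining clinic in exploratory models does not alter the primary estimate, confidence interval or p-value.

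The consequence depends on how allocation is done within site. The protocol calls the scheme simple and mentions no blocks.

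- **Unblocked within site.** The printed test is valid, but its estimate is less precise than it could be whenever site predicts the outcome.
- **Blocked within site.** The design already balances arms across sites, so the estimate is as precise as it would be with site in the model. The model-based standard error is too large, however, because between-site variation stays in the residual. The test is then conservative.

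Neither case inflates type I error. What is at stake is a modest amount of power and interval width.

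**Working it through.** **Inputs from the documents.** 337 per arm at six months (674 analysed); a figure of 1.9 described as variances; detectable difference 0.43 at 80% power, two-sided 5% (Power and Sample Size Considerations); six sites (Study Sites).

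**Inputs assumed.** Site share of the residual variance after baseline, s = 2%, 5% or 10%, with zero as the limiting case. Correlation of baseline with six-month HbA1c, r = 0.3 to 0.5. The documents give neither.

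**The plan's own figure.** Detectable difference = (1.960 + 0.842) × SD × √(2/337).
- 1.9 as an SD: 2.802 × 1.9 × 0.0770 = 0.41.
- 1.9 as a variance (SD 1.378): 2.802 × 1.378 × 0.0770 = 0.30.

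Neither equals the stated 0.43. The SD reading is closer, so it is used for power below. The relative standard errors do not depend on this choice.

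**Blocked allocation.**
- SE ratio, without site to with site = 1/√(1 − s).
- Type I error without site = 2 × [1 − Φ(1.96/√(1 − s))].
- Equivalent patients lost = 674 × s.

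**Unblocked allocation.** Adjusting for site carries a small cost from chance imbalance of arms across sites. The variance inflation is 1 + 5/(674 − 8) = 1.0075, or 1.0037 on the SE.
- Net SE ratio = 1/√[(1 − s) × 1.0075].
- Equivalent patients lost = 674 × [1 − (1 − s) × 1.0075].

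| Site share s | Blocked: SE ratio | Blocked: type I error without site | Blocked: patients lost | Unblocked: SE ratio | Unblocked: patients lost |
|---|---|---|---|---|---|
| 2% | 1.010 | 0.048 | 13 | 1.006 | 9 |
| 5% | 1.026 | 0.044 | 34 | 1.022 | 29 |
| 10% | 1.054 | 0.039 | 67 | 1.050 | 63 |

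**Break-even (unblocked).** 1 − 1/1.0075 ≈ 0.7%. Below that share, adding site loses a little precision, at most about 0.4% in SE. The five degrees of freedom hardly matter: the critical t is 1.964 at both 671 and 666.

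**Power at a true difference of 0.43, SD 1.9, unblocked.** The SE without site is 1.9 × √(2/337) × √(1 − r²), which is 0.1396 at r = 0.3.

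| r | Without site | With site, s = 2% | s = 5% | s = 10% |
|---|---|---|---|---|
| 0.3 | 86.9% | 87.3% | 88.2% | 89.9% |
| 0.4 | 89.3% | 89.7% | 90.6% | 92.0% |
| 0.5 | 92.4% | 92.7% | 93.4% | 94.5% |

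The gain is about 0.3 to 3 points. Under blocking it is 0.3 to 2.0 points. If 1.9 is a variance, power at 0.43 is already near its ceiling and every gain is under 0.5 point.

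**Simulation check.** 674 patients, six unequal sites of 60 to 170, r = 0.4, SD 1.9, 8,000 runs per setting, Monte Carlo error about ±0.005. Values are for s = 2%, 5% and 10% in turn.
- Type I error without site, blocks of four: 0.047, 0.047, 0.037.
- Type I error without site, unblocked: 0.053, 0.051, 0.046.
- Type I error with site, all settings: 0.046 to 0.052.
- Mean SE, unblocked, without site: 0.1342, 0.1343, 0.1344.
- Mean SE, unblocked, with site: 0.1334, 0.1314, 0.1279.
- Mean SE at s = 0, unblocked: 0.1343 without site, 0.1348 with it.

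These agree with the formulas.

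**The case against.** The strongest reply is that no error has been shown. The printed test is valid if allocation is unblocked and slightly conservative if blocked, so the point is a preference for a more efficient model. That is correct, and it is why the point is not graded as a validity problem.

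The gain is also unproven. The documents give no between-site variance, and the remark about diverse practices concerns size, staffing and patient mix, not six-month HbA1c after baseline adjustment. Eligibility confines recent HbA1c to 7.5–10% and baseline is already in the model, so the site share could be small. The 3-point figure needs a 10% share, r = 0.3 and unblocked allocation together; at a 2% share the gain is 0.3 to 0.4 point. All of this stands. Against it, the loss is capped at about 0.4% in SE, while the gain reaches about 5% over the assumed range.

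On the unblocked reading, nothing in the design forces site into the analysis, and site is an ordinary covariate. That also stands, but it remains a pre-specifiable covariate that the trial already records for everyone. The blocked figures assume exact balance among analysed patients. With a 10% share and 10% random loss, type I error moves only from 0.039 to about 0.040.

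Finally, clinic is not ignored: baseline is summarised by clinic and exploratory clinic models are planned. Those would reveal site differences but leave the primary result unchanged. The calculations cover HbA1c only; extending the model to other outcomes rests on the same reasoning, without figures for them.

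**Conclusion.** The concern holds. Site stratifies randomisation and is missing from the primary model, and nothing elsewhere in the plan puts it there. Omitting it makes the standard error about 0.6% to 5.0% larger (unblocked) or 1.0% to 5.4% larger (blocked) if site explains 2% to 10% of the residual variance. That range is an assumption, and the true gain may be small or nil. Type I error is not inflated under either allocation scheme. This is a nearly free improvement of low to moderate priority that should be made; the trial's conclusions do not depend on it.

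**What to change.** In Data Analysis, Aim 1, define the primary model as six-month HbA1c regressed on arm, baseline HbA1c and site, with site as five fixed indicators. Use the same form (arm, baseline value, site) for the other H1–H6 outcomes. This model is valid whether or not allocation is blocked within site, so the allocation method need not be settled first. The random clinic effect can stay as a sensitivity analysis.

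As a minor clarification, add one sentence saying that this model gives the primary result and that models adjusted for baseline variables found significant are supportive. The text already leans that way but never states their status.

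The cost is SAP wording only, best changed before outcome data are analysed: no new patients, data or procedures, five of about 671 residual degrees of freedom, and at most about 0.4% in standard error if site proves irrelevant.
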